The couples will be recruited from the list of women who are receiving BISP-CT and meet the eligibility criteria of: adult married women who: receive BISP-CT, have one child of at least 18 months and have no family migration plan for next 2 years.

The couple in which either of the partners has gross mental impairment, physically challenged or bedridden, will be excluded.

Sample Size

There will be three groups for cRCT. The first group will receive LSB to BISP-CT beneficiaries and their husbands. The second group will receive LSB only to women receiving BISP-CT. The third group will be the control arm who will receive BISP-CT only. Assuming an average cluster size of at least 25 couples, with the baseline prevalence of depression 60% and expected reduction of 20% in intervention arm, 9 clusters per arm would be needed over a period of two years. There are three arms and 9 clusters in each arm so a total of 675 couples (225 in each arm, 25 in each cluster). By accounting for the attrition rate of 25%, a minimal of 846 couples (282 per arm) would be needed.

Sampling Strategy

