The implementation of the manualized LSB curriculum will be delivered through 10-12 sessions (10 for couples, 2 for family including mother-in-law, supporter or head of the household), one session per week for each cohort of 282 couples. Therefore, for three cohorts, a total of 846 couples, will require nine months. There will be 12 LSB teachers (8 females, 4 males) working in six pairs for six groups (4 women, 2 men) for the entire year. The purpose is to ensure high quality staff, optimum delivery of the intervention between the cohorts, and proper fidelity monitoring. Regarding the data collection plan, the data collection points are pre-intervention (baseline) and post-intervention (end-line, five months). The schematic illustration is mentioned below in figure 4.

[figure not shown]
Safety protocols amid COVID 19

Capacity building of the research team will be carried out, where a comprehensive COVID-19 awareness training will be offered to the field team. The field preparations will include; adequate supply and use of PPEs (face masks, sanitizers), information communication material (in local language) to be used in field office and community settings. Furthermore, the team will work closely with the DC office Thatta to obtain the list of nearby health facilities assigned by the provincial government to provide COVID-19 screening, testing, isolation/quarantine, treatment/referral in the study area. This exercise will ensure the safety and wellbeing of staff and community participants, before the actual delivery of LSB intervention in the study area.

Moreover, to ensure the wellness of field staff, an orientation regarding the use of CoronaCheck; a new mobile app that enables them to easily and safely evaluate symptoms with an in-home screening tool and understand the next steps they need to take to look after themselves, will be provided. The app allows the staff to understand their symptoms, identify whether they may have contracted COVID-19 and seek help in a timely manner. It also helps the staff to identify potential coronavirus carriers and limit their risk of transmission. It will be assured that, the staff should use the app on daily basis as they come to office and contact AKU employee health service for initial screening and if needed testing.

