The revised conflict tactics scale consists of 20-item and is self-administered. The scale includes items regarding Negotiation (1-4), Psychological aggression (5-8), Physical assault (9-12), Sexual coercion (13-16) and Injury (17-20). The scoring criteria consists of a scale from 1-8, 1-6 indicates the frequency of conflict happened in the past year ranging from once to more than 20 times. 7 indicates conflict happened not in the past year but happened before that. If it never happened, 8 will be marked (Douglas & Straus, 2004). There are many ways to score the CTS: Respondents who reported being a victim of or perpetrating an item or items (Prevalence). The number of times an item occurred in the past year (Frequency). Classifying each case into three categories: none, minor only, or severe (severity level). Classifying each case as respondent only, partner only, or both (mutuality types). For this study, Sindhi translated version will be used after pre-testing.

Patient Health Questionnaire (PHQ-9)

The Patient Health Questionnaire (PHQ) is a self-administered instrument for common mental disorders. The PHQ-9 is the depression module, which scores each of the 9 DSM-IV criteria as "0" (not at all) to "3" (nearly every day). It is used to monitor the severity of depression and response to treatment. It can be used to make a tentative diagnosis of depression in at-risk population (Kroenke, Spitzer, & Williams, (2001). For this study, the Urdu adaptation of the PHQ-9 tool will be used (Ahmad et al., 2018). This tool has been translated into Sindhi language and will be used in this study. PHQ-9 total score for the nine items ranges from 0 to 27. Scores of 5,

10, 15, and 20 represent cut points for mild, moderate, moderately severe and severe depression, respectively.

The Resilience Scale (RS-14)

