To avoid possible human error of missed or incorrect entries, the entered data will be cross checked initially by data coordinator, and discussed with research team and principal investigators, if required. All the data will be double entered in Excel, followed by congruence check and cleaning. It will be imported to STATA version 12.1 for the analysis, after cleaning.

Descriptive Statistics: Descriptive statistical analysis will be run to look at the distribution of variables of interest and for outcome variables. Mean and standard deviation will be calculated for continuous variables, proportions will be calculated for the categorical variables.

Logistic regression will be used to assess the effect of LSB with maternal depression and other outcomes. All variables meeting the criteria will be used for building the final model. The variable found most significant in the univariate analysis will be subsequently added first and the next significant variable one after the other. Variables found statistically non-significant (>0.05), biologically not meaningful will be removed from the model. Multivariate logistic regression will be carried out to reach to the most parsimonious model.

Communication Plan and Stakeholder Management

The project team will involve stakeholders at multiple levels. At national, coordination with BISP office in Islamabad and other relevant programs on maternal and child health will be carried out to sensitize them about the study scope and the outcomes and their implications on policy. Study team will meet regularly in coordination with Umeed-e-Nau program management over the study period and will discuss the project implementation.

Local stakeholders will include the BISP offices in Sindh province. Regular coordination is needed with the provincial office Local Health Department in the study will also be presented the results. Biannual meetings will be set with local stakeholders to share research progress and milestones.

Monitoring and Evaluation Plan

The primary responsibility for monitoring the fidelity of the intervention delivery will rest with Aga Khan University and they will be required to ensure that a log sheet is kept recording the trainings conducted by faculty of AKU to train LSB teachers and number of couples who attended the training. This information will be reported quarterly to Principal Investigators. The information

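### Depression is tested only as present or absent although the 0-27 PHQ-9 score is collected twice, which costs precision: roughly 15-33% of the information in clusters of 25, under stated assumptions

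*Protocol*

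**What the plan says.** Depression is a primary outcome and the only one that enters the sample size. The Sample Size section treats it as a proportion: "with the baseline prevalence of depression 60% and expected reduction of 20% in intervention arm, 9 clusters per arm would be needed", with 25 couples per cluster and so 225 per arm.

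The instrument is the PHQ-9. Under Assessment Tools the protocol says "PHQ-9 total score for the nine items ranges from 0 to 27", and of its purpose: "It is used to monitor the severity of depression and response to treatment". Scores of 5, 10, 15 and 20 "represent cut points for mild, moderate, moderately severe and severe depression, respectively"; the protocol does not say which of them defines a depressed woman.

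On timing, the Operational Plan says "the data collection points are pre-intervention (baseline) and post-intervention (end-line, five months". Each woman followed to end-line therefore has two scores.

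On analysis, the Data Analysis section says: "Logistic regression will be used to assess the effect of LSB with maternal depression", and the same sentence extends the method to the other outcomes. Continuous variables appear only under descriptive statistics: "Mean and standard deviation will be calculated for continuous variables, proportions will be calculated for the categorical variables". Covariates enter the logistic model one at a time according to univariate significance. Baseline PHQ-9 is not named as a covariate, and no between-arm analysis of the score is described.

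**The concern.** A yes/no analysis ignores all movement that does not cross the chosen line. Take a cut-point of 10 as an illustration: a woman who goes from 20 to 10 is still counted as depressed, while a woman who goes from 10 to 9 counts as a full response. The protocol itself presents the scale as a measure of severity and response, which is the information that the split removes.

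With 9 clusters per arm, precision is scarce. The score is already being collected, so a more precise test of the same question needs no extra couple, visit or instrument. What is at stake is power on the outcome that the trial is sized on.

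**Working it through.** **Inputs from the protocol.** Starting prevalence 60%; a reduction of 20%, not said to be relative (60 to 48%) or absolute (60 to 40%); 9 clusters of 25, so 225 per arm; PHQ-9 total 0-27, measured at two times.

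**Assumptions, because the protocol gives no figure.** Two-sided alpha 0.05; a normal score that shifts as a whole; score ICC 0.01 to 0.10; baseline/end-line correlation 0.5 where baseline is used.

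**1. The plan's own figure.** Alpha, power and ICC are not stated, so the 9 clusters can only be matched, not verified. At 80% power, 60 to 40% needs 97 women per arm before clustering. With ICC 0.05 the design effect is 1 + 24 × 0.05 = 2.2, and 97 × 2.2 / 25 = 8.5 clusters, which rounds up to 9. For 60 to 48%, 270 per arm are needed before any clustering, already more than 225.

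**2. Loss per independent woman.** The efficiency of splitting a normal score at proportion p is φ(z_p)² / [p(1 − p)]. At p = 0.6, z = 0.2533 and φ = 0.3863, so 0.3863² / 0.24 = 0.622, a loss of 37.8%. The same loss seen as sample size (80% power, no clustering):

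- 60 to 48%: the matching shift is 0.253 + 0.050 = 0.304 SD; 270 women per arm (binary) v 171 (score).
- 60 to 40%: the shift is 0.253 + 0.253 = 0.507 SD; 97 v 62.

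**3. Loss in clusters of 25.** Splitting the score also lowers its ICC, which recovers part of the loss. The binary ICC follows from the bivariate normal at the 60% cut. Efficiency = 0.622 × (1 + 24 × ICC_score) / (1 + 24 × ICC_binary).

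| Score ICC | Binary ICC | Efficiency | Loss |
|---|---|---|---|
| 0.01 | 0.0062 | 0.671 | 33% |
| 0.02 | 0.0124 | 0.709 | 29% |
| 0.03 | 0.0187 | 0.739 | 26% |
| 0.05 | 0.0312 | 0.783 | 22% |
| 0.10 | 0.0625 | 0.846 | 15% |

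For ICC 0.05: 0.622 × 2.2 / 1.749 = 0.78.

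**4. Power by simulation.** 9 v 9 clusters of 25, the same latent score behind both outcomes, cluster-level t tests on 16 degrees of freedom. The adjusted columns use baseline PHQ-9 for both outcomes. Repeat runs agree to within about two points.

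| Drop, score ICC | Binary | Score | Binary, adjusted | Score, adjusted |
|---|---|---|---|---|
| 60 to 48%, 0.03 | 52% | 64% | 61% | 76% |
| 60 to 48%, 0.05 | 46% | 55% | 54% | 66% |
| 60 to 40%, 0.03 | 92% | 97% | 96% | 99% |
| 60 to 40%, 0.05 | 86% | 92% | 93% | 98% |

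Like for like, the score gains 9 to 15 points for 60 to 48%, and 3 to 6 points for 60 to 40%.

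**5. Non-normal scores.** Negative binomial scores capped at 27, without clustering, gave an efficiency of 0.481 to 0.639, a loss of about 36% to 52%. Skewness does not remove the problem.

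**The case against.** The strongest reply is that the protocol is consistent. The Hypothesis section claims a 20% reduction, the sample size is built on prevalence, and logistic regression estimates an effect on that outcome. Prevalence is also easy to use for policy. This stands: a reader might infer that the binary analysis contradicts the plan or is invalid, and the documents do not support that. It also means that replacing the headline test is a debatable preference.

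On size, three inferences go too far.

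- Taking 38% as the loss in this trial. That figure is for independent women; with villages of 25 the loss is smaller.
- Applying one design effect and a normal quantile to both outcomes. For 60 to 48% at ICC 0.03-0.05 this gives 50-41% v 69-58%, gaps of 19 and 17 points where the simulation shows 12 and 9.
- Setting an unadjusted binary test beside a baseline-adjusted score (52-46% v 76-66%). Part of that gap comes from baseline adjustment, which a logistic model can also use.

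If the 20% is absolute, binary power is already 86-92% unadjusted and little is gained. That also stands, but the protocol does not say which reading it means.

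Finally, an analysis plan that is not shown may add a score model. That is possible, but the point does not rest on silence: the protocol names the method for depression, and that choice is what is questioned.

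**Conclusion.** The point holds as a loss of efficiency. Under a normal score the loss is about 38% per independent woman and roughly 15-33% in clusters of 25 for score ICC 0.10 to 0.01. In power, at ICC 0.03-0.05, it matters if the planned effect is 60 to 48% (9 to 15 points, at a level where neither unadjusted test reaches 80%) and is modest if it is 60 to 40% (3 to 6 points). These figures rest on an assumed normal shift, two-sided 0.05, the ICC range and, for the adjusted comparison, a correlation of 0.5; none of these is given in the protocol. The direction was the same in every scenario tried. The change is worth making because the data are already in hand, not because the stated analysis is wrong.

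**What to change.** In the Data Analysis section:

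- Keep the prevalence of depression by arm, with its risk difference, as the result that answers the 20% claim.
- Prespecify, as a key analysis beside it, the end-line PHQ-9 total score adjusted for baseline PHQ-9, with arm as a factor and cluster as a random effect.
- Adjust the binary model for baseline PHQ-9 as well, as a fixed covariate and not subject to selection by significance.

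The cost is one more model on data already collected. The added effect is expressed in PHQ-9 points, which is less direct than a percentage, and a skewed score may call for robust or bootstrap standard errors.

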The health status of a woman is only improved, if special emphasis is given to her mental health. As a result of improvement in mother's mental health the entire family will be less stressed and can obtain better cohesion and higher functioning. Although research evidence indicates an association between women's mental health and domestic violence, the existing knowledge on associations between women's mental health determinants, economic development and child health outcomes is still unclear. The link between mental health and low income amongst urban women has been well documented in developing countries (Blue, Ducci, Jaswal, Ludermir, & Harpham, 1995). Research evidences point out that low socio-economic status assessed by

maternal standard of living is consistently associated with a higher prevalence of depression and other mental health related morbidities in cross sectional studies (Lorant et al., 2003).

Moreover, women's mental wellbeing is closely linked to many other core components such as: financial independence, family harmony, empowerment and self-efficacy. A number of studies have supported counseling as an intervention utilizing group approach for problem solving thus reducing depression and stress, thus fostering effective interpersonal skills. Microfinance and cash transfer have proved to be a successful intervention in many developing countries, leading to increased household economic wellbeing, greater food security, increased children school attendance, gender equity, women empowerment, self-confidence, communication and reduction in the vulnerability of violence among women and their children (Paul, 2006 & Duvendack et al 2011). Interventions in developing countries have shown effectiveness of life skills training for enhancing communication and assertive skills, decision-making, building self-esteem, self-efficacy, reducing learning difficulties, decrease aggressive behavior, anger control, and changing attitudes towards engaging in sexual behavior (Ahmed, Petzold, Kabir, & Tomson, 2006; Naseri, A., & Babakhani; Maryam, Davoud, & Zahra, 2011). There is a dire need to empower women through programs such as cash transfer and LSB to reduce poverty, depression and violence.

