The aim of this research is in line with the 2030 agenda for Sustainable Development Goals. This agenda is a plan of action to strengthen universal peace and recognizes poverty as the greatest hurdle in sustainable development. The first goal of this document is concerned with a step of reducing poverty and the second goal aims to bring the efforts for gender equality by empowering women. Through BISP-CT intervention, it is hoped that the overall economic wellbeing of the women and their families will improve and through LSB, women will become more empowered. Ultimately they will be able to compete in the world as global citizen alongside men (Agenda for Sustainable Development, 2030). This study aims to engage men in women empowerment (MEWE) through LSB and BISP-CT to improve maternal mental health in Pakistan using a randomized control trial.

Primary Objectives

To measure the impact of men engagement in LSB and CT on maternal depression, domestic violence, improved self-efficacy and women empowerment.

Secondary Objectives

To measure the impact of men engagement in LSB and CT on Household food security, Gender Attitude, Economic Solvency and Resilience.

Primary Outcomes

Reduced maternal depression, domestic violence, improved self-efficacy and women empowerment.

Secondary Outcomes

Improved household food security, gender attitude, economic solvency and resilience.

Method

Program Implementation and Approach

The proposed study areas for the Formative Phase of the project are Punjab (Rahimyar Khan), Balochistan (Lasbela), Khyber Pukhtunkhuwa (Peshawar) and Sindh (Thatta). The cRCT will be conducted in district Thatta.

Key Intervention

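### The model-building rule for the LSB effect selects covariates by p-value from an undefined pool, does not limit them to baseline and does not keep the arm in the model

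*Protocol*

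**What the plan says.** All of this stands in the Data Analysis section that follows Assessment Tools, not the qualitative one in Phase 1.

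- Purpose of the model: "Logistic regression will be used to assess the effect of LSB with maternal depression and other outcomes".
- Candidate pool: "All variables meeting the criteria will be used for building the final model". The criteria are not stated here or elsewhere.
- Order of entry: "The variable found most significant in the univariate analysis will be subsequently added first and the next significant variable one after the other".
- Removal: "Variables found statistically non-significant (>0.05), biologically not meaningful will be removed from the model".
- Target: "Multivariate logistic regression will be carried out to reach to the most parsimonious model".

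Three other places bear on it. The Operational Plan collects data at baseline and at a five-month end-line. Primary Outcomes lists depression together with violence, self-efficacy and empowerment: "Reduced maternal depression, domestic violence, improved self-efficacy and women empowerment". Secondary Outcomes lists food security, gender attitude, economic solvency and resilience.

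On links between these variables, Background and Introduction describes depression as often following from domestic violence. The section on economic empowerment and maternal mental health says that women's "mental wellbeing is closely linked to many other core components such as: financial independence, family harmony, empowerment and self-efficacy".

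**The concern.** This rule governs the estimate of the randomised effect. It is not a side analysis of risk factors. Two features are unsafe for that purpose.

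First, the pool has no time limit. Each scale is scheduled at baseline and at end-line, so end-line scores will be in the dataset. The only stated filters are significance and biological meaning, and end-line violence or self-efficacy could pass both. They are also outcomes that LSB is meant to change. A model that conditions on them no longer estimates the effect of being randomised to LSB; it estimates what remains once those pathways are held fixed. As the rule covers depression and the other outcomes alike, the same could happen with each outcome in turn as the dependent variable.

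Second, the arm is not protected. If it is treated like any other variable, it can be removed when its p-value exceeds 0.05, and the final model then carries no treatment estimate.

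At stake are the meaning, the size and even the presence of the treatment coefficient for the primary outcomes.

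**Working it through.** **Inputs from the protocol (Sample Size).** 9 clusters × 25 couples = 225 per arm. Depression is 60%, with a 20% reduction. The text does not say whether this is relative (60 × 0.8 = 48%) or absolute (60 − 20 = 40%), so both are shown. No figure in the plan states the point at issue, so there is none to reproduce.

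**Reference values without adjustment or clustering.**
- OR, 60% to 48%: (0.48/0.52) / (0.60/0.40) = 0.923/1.5 = 0.615.
- OR, 60% to 40%: (0.40/0.60) / 1.5 = 0.444.
- Power at 225 per arm, two-sided 0.05: 72.5% and 99.0%.

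**Simulation of the rule.** One LSB arm against control, 225 per arm, 300 runs per setting. Depression is a latent score of unit variance, cut so that 60% of controls are depressed. Two baseline covariates have coefficient 0.2 each, and three independent end-line variables 0.3 each, leaving residual variance 1 − 3(0.09) − 2(0.04) = 0.65. An assumed share of the arm effect runs through the end-line variables. Candidates with univariate p ≤ 0.05, including the arm, enter strongest first; terms with p > 0.05 are removed. The OR is taken with the arm put back beside the selected covariates, so it exists even in runs where the rule drops the arm.

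60% against 48%:

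| Share through end-line variables | OR, baseline candidates only | Arm kept | OR, end-line candidates added | Arm kept |
|---|---|---|---|---|
| 0% | 0.59 | 72% | 0.52 | 73% |
| 25% | 0.61 | 69% | 0.63 | 55% |
| 50% | 0.59 | 75% | 0.72 | 31% |
| 75% | 0.60 | 73% | 0.85 | 13% |
| 100% | 0.60 | 66% | 1.00 | 2% |

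60% against 40%:

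| Share through end-line variables | OR, baseline candidates only | Arm kept | OR, end-line candidates added | Arm kept |
|---|---|---|---|---|
| 0% | 0.43 | 100% | 0.35 | 100% |
| 25% | 0.42 | 99% | 0.45 | 94% |
| 50% | 0.42 | 98% | 0.58 | 64% |
| 75% | 0.43 | 98% | 0.78 | 17% |
| 100% | 0.42 | 99% | 1.00 | 4% |

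With 300 runs, a retention of 31% has a standard error of √(0.31 × 0.69/300) = 2.7 points.

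**Reading the tables.** Two forces act. Conditioning on a strong correlate of a binary outcome moves the odds ratio away from 1 (0.59 to 0.52 when nothing is mediated), because odds ratios are not collapsible. Taking out the mediated part moves it towards 1. At a share of 25% the two roughly cancel in the OR, though the arm is kept less often (55% against 69%). At one half the second force dominates.

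**Cross-check.** A second simulation of the rule, with a single end-line variable of coefficient 0.5, gave for 60% against 48% at a share of one half an OR of 0.58 moving to 0.70, with the arm kept in 31% of runs instead of 79%. At shares of 0 to 25% the OR was 0.54 to 0.63 against about 0.60.

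**The case against.** The strongest reply is that the protocol never says end-line scores will be covariates. It admits variables that meet criteria, and the list of eligible covariates with their time points is normal content for a statistical analysis plan, which is not at hand. The scales concerned are named as outcomes, so the natural reading makes them dependent variables. This stands in part: end-line adjustment is permitted by silence and not prescribed, and a reader who infers that the rule admits every variable drops its qualifier. It does not clear the paragraph, because the protocol itself fixes significance-driven selection for the effect model, and a plan limiting covariates to pre-specified baseline variables would have to replace that text.

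Three stronger readings are tempting and are not supported.

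- *All end-line scales are stated pathways to depression.* The protocol supports this for violence, and loosely for self-efficacy, where it states an association. It states no such link for resilience or food security.
- *End-line scores would enter first.* This is plausible for measures taken at the same visit, but no figure ranks them, and baseline PHQ-9 is an obvious competitor.
- *The effect is biased towards none.* This is not unconditional: with nothing mediated the OR moves the other way.

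The removal sentence is also loosely worded. If a variable must be both non-significant and not meaningful to be removed, the arm might survive on judgement. The text does not say so, and the ORs above do not depend on the arm surviving.

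Finally, the mediated shares and coefficients are assumptions, and clustering is left out, so the retention figures are illustrations and not forecasts for this trial.

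**Conclusion.** The point holds in a limited form. The rule that produces the LSB estimate selects on p-values from an undefined pool, sets no baseline limit and does not protect the arm. Applied as written, it can condition on consequences of LSB and can drop the arm.

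The damage is conditional. If about half or more of the effect on depression runs through end-line variables that enter the model, the OR for 60% against 48% moves from about 0.6 to about 0.7 or nearer 1, and the arm is kept in about 31% of runs or fewer instead of about 70%. For 60% against 40%, a share of one half moves the OR from 0.42 to 0.58 and retention from 98% to 64%. At a share of 25% or less the OR is not attenuated. These figures assume 225 per arm, no clustering, the stated coefficients and removal of the arm at p > 0.05. The absence of a baseline limit and of a protected arm term rests on the text alone and needs none of these assumptions.

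**What to change.** Replace the selection rule in Data Analysis with text such as:

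*The effect model always retains the randomised arm and adjusts only for pre-specified variables measured at baseline, including the baseline value of the outcome; covariates are not selected by p-value. Any model with end-line scores is labelled exploratory mediation analysis.*

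The covariates should be named before end-line data are seen, in the protocol or in the statistical analysis plan. Restricting the pool to baseline would not be enough by itself, since it would leave p-value selection and the unprotected arm in place.

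The cost is some flexibility in model building. The baseline assessments are already scheduled, so no new data or staff are needed.

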Since men are frequently neglected in global health programs to improve maternal and child health, the BISP-CT plus LSB proposal for "couples" is an innovative strategy to test the involvement of men towards better maternal and child health. The extent of major maternal health deficits in Pakistan cannot be stressed enough; therefore, involving men is the new initiative which is being tested in this project. Previously mixed results were obtained in terms of reducing poverty and violence against women when BISP-CT & LSB were administered specifically to women only. Through the addition of men, the impact of LSB is proposed to be enhanced. Furthermore, the proposed study not only measures women empowerment alone but also couples' empowerment through the interventions mentioned above. The purpose is to improve maternal and child health by empowering women through LSB training to BISP beneficiary married couples.

Problem Statement

Women in Pakistan are deprived of basic human rights of education, health and economic independence. Women remain dependent on their husbands, financially and socially.

Studies conducted in other part of the world have supported CT and LSB to reduce poverty, depression and violence. Recently, the negative consequences of maternal depression on children have also been well documented.

Situational Analysis

The current situation of women in Pakistan due to financial dependence and poor life skills, as described above, makes the role of our research more imperative in combating this issue through innovative interventions.

More specifically, the scope of this project is to improve maternal mental health by decreasing depression, empowering women economically and psychosocially so that they can prevent their victimization from violence and improve their health and family. Since children brought up in a healthy environment will grow up to build stronger families and hence the vicious cycle of continuing violence can be interrupted and stopped.

Therefore there is a need to test the interventions related to financial enhancement with LSB training to decrease maternal morbidity (depression), domestic violence, increase women financial empowerment, maternal and child health and nutrition.

Hypothesis

Introduction of LSB to BISP-CT beneficiaries in couples will reduce domestic violence and depression in married women of reproductive age by 20% and improve women empowerment by 20%.

Aim and Objective

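### The only inferential model is stepwise logistic regression driven by p-values, and the text does not set the randomised arm apart from the covariates

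*Protocol*

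**What the plan says.** The Data Analysis section that follows Assessment Tools first covers data entry and descriptive statistics. It then gives a single inferential procedure, in five consecutive sentences:

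- Purpose: "Logistic regression will be used to assess the effect of LSB with maternal depression and other outcomes".
- Candidates: "All variables meeting the criteria will be used for building the final model". The criteria are not given.
- Entry: "The variable found most significant in the univariate analysis will be subsequently added first and the next significant variable one after the other".
- Removal: "Variables found statistically non-significant (>0.05), biologically not meaningful will be removed from the model".
- Goal: "Multivariate logistic regression will be carried out to reach to the most parsimonious model".

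No other analysis of the intervention effect appears in the protocol. No sentence says that arm is held in the model or that selection is confined to covariates.

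The primary objective is "To measure the impact of men engagement in LSB and CT on maternal depression, domestic violence, improved self-efficacy and women empowerment". The Rationale adds "Through the addition of men, the impact of LSB is proposed to be enhanced". Both are comparisons between randomised arms.

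**The concern.** Selection by p-value towards a parsimonious model suits exploratory risk-factor work. In a randomised comparison the arm contrasts are the result, and they are needed whatever their p-values. Because the section uses one set of rules for both tasks, two analysts could follow it faithfully and report different things. One would give an adjusted arm effect for every outcome. The other would give one only where arm was significant, and adjusted effects reported on that condition tend to be too large when the true effect is modest.

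This is not a detail that the protocol merely leaves to a SAP. It fixes a rule, and a SAP that kept arm regardless would have to override or reinterpret that rule.

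**Working it through.** **Step 1: what happens to arm under each reading.** The removal sentence joins two conditions with a comma, so it is open whether both are needed or one is enough.

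| Reading | Fate of a non-significant arm |
|---|---|
| Arm is the exposure; selection applies to covariates only | Stays |
| Arm enters; removal needs both conditions | Stays, since the intervention is hardly biologically meaningless |
| Arm enters; either condition is enough | Removed at p>0.05 |
| Arm must also pass univariate screening | May never enter (entry threshold not stated) |

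In the last two rows the crude univariate estimate remains.

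**Step 2: inputs for an illustration of the literal reading.**

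- 9 clusters × 25 = 225 per arm, and 60% baseline depression (Protocol, Sample Size).
- Effect: "with the baseline prevalence of depression 60% and expected reduction of 20% in intervention arm, 9 clusters per arm would be needed". The 20% may be absolute (60 − 20 = 40%) or relative (0.8 × 60 = 48%).
- Removal threshold 0.05 (Data Analysis).
- Assumed: women-only rate at the midpoint (50% or 54%), and ICC 0 to 0.05. The protocol gives neither.

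Rates below are couples/women-only/control.

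**Step 3: ICC 0, by formula.** Test arm as one three-level term in ordinary logistic regression, with a 2-df Wald test and critical value 5.99. The noncentrality is λ = Σ wᵢ(lᵢ − l̄)², where wᵢ = 225·pᵢ(1−pᵢ), lᵢ = logit(pᵢ) and l̄ is the weighted mean.

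- 40/50/60%: w = 54, 56.25, 54; l = −0.405, 0, 0.405; l̄ = 0. λ = 2 × 54 × 0.4055² = 17.76, so P(p>0.05) = 2.7%.
- 48/54/60%: w = 56.16, 55.89, 54; l = −0.080, 0.160, 0.405; l̄ = 0.159. λ = 3.20 + 0.00 + 3.29 = 6.49, so P(p>0.05) = 38%.

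**Step 4: with clustering in the data but not in the test.** 40,000 simulated trials per setting, arms only:

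| True rates | ICC 0 | ICC 0.02 | ICC 0.05 |
|---|---|---|---|
| 40/50/60% | 2.5% | 4.5% | 7.0% |
| 48/54/60% | 36.9% | 35.5% | 34.6% |
| No effect (60/60/60%) | 95.1% | 87.1% | 74.4% |

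A repeat run with beta-distributed cluster rates agreed within one percentage point. In trials where arm is retained, the mean couples v control log odds ratio is 1.22 to 1.29 times too large at 48/54/60% and 1.01 to 1.05 times at 40/50/60%.

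The midpoint is an unfavourable assumption. If women-only does as well as couples, the figures are 24% to 26% (48/48/60%) and 0.4% to 3% (40/40/60%).

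**Step 5: what these figures are.** No covariates are in this run, so the crude and adjusted models coincide, and the entries are simply one minus the power of the test. The fall from 95% to 74% under no effect comes from ignoring clustering, not from selection. A separate, smaller run that did apply stepwise selection, with assumed covariates, found arm absent in 1% to 6% (40/50/60%) and 31% to 41% (48/54/60%) of trials.

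**Step 6: which effect size fits the design.** At an assumed 80% power and two-sided 5%, with d = p₁ − p₂, n = [1.96√(2p̄q̄) + 0.84√(p₁q₁ + p₂q₂)]²/d². For 60 v 40%, n = 97 per arm; for 60 v 48%, n = 270, both before clustering. The planned 225 covers the first with room for a design effect and falls short of the second. The smaller figures in Step 4 therefore fit the design better.

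**Step 7: if arm is always kept.** In simulation at ICC 0 with assumed covariates, confidence-interval coverage was 94% to 97% with selected covariates and 93% to 96% with fixed ones (Monte Carlo standard error about 0.9 points). That shows no measurable loss. No single covariate set was chosen in more than 25% of trials.

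**The case against.** The strongest reply is that the opening sentence names LSB as the exposure. A model meant to assess LSB cannot do so without it, so the selection sentences are naturally read as being about other variables. Read jointly, the two removal conditions would not drop the intervention either. This stands as the likelier intent, but it is not written.

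It is also fair that the crude arm estimate survives on any reading, and that under randomisation it is a legitimate comparison, provided its standard error allows for clusters. The result would not be lost. What would be missing is its adjusted form.

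Three stronger inferences are tempting, and the documents do not support them:

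- That the plan will delete the arm. This needs one particular reading of an ambiguous comma, or an entry screen applied to arm.
- That the women-only and control arms would be pooled. This needs arm to be coded as two separately tested indicators, and the protocol states no coding.
- That 35% to 37% measures the harm of stepwise selection. It is the chance of a non-significant test under assumed rates, and it belongs to the effect size that fits the sample size less well.

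Finally, a covariate list is commonly left to a SAP. That is so, but here the protocol commits to choosing covariates by p-value.

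**Conclusion.** The point holds as a badly fixed rule with an ambiguity in it; minor to should-fix. The section makes p-value-driven selection the only route to an estimated effect of LSB and does not protect the randomised arm.

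- **Literal reading:** a non-significant arm is missing from the adjusted model. For scale only, that is about 2% to 7% of trials at 40/50/60% and about 35% to 37% at 48/54/60%. These ranges rest on an assumed ICC of 0 to 0.05, an assumed women-only rate and a test that ignores clustering.
- **Likelier reading, arm kept:** coverage showed no measurable harm. What remains is that covariates are picked after seeing the data and can differ across the four primary outcomes. The two most natural adjusters, UC and the baseline outcome, are in the model only if they survive selection.

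**What to change.** Replace the stepwise paragraph with one model per outcome, fixed in advance. It should always contain:

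- arm as a three-level factor, exempt from screening and removal;
- UC, because Sampling Strategy keeps the number of clusters per arm equal within each UC;
- the baseline value of that outcome, which the Operational Plan already collects.

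Use standard errors that allow for the randomised clusters. Report the arm contrasts with confidence intervals whatever their p-values. Keep stepwise selection for exploratory risk-factor work.

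The minimum is one sentence stating that arm is never screened or removed and that selection applies to covariates only. This removes the ambiguity but leaves the covariate set chosen from the data.

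The cost is a wording change with no new data. The downside is that prognostic covariates not named beforehand are no longer adjusted for.
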